2.6. IMGC936 Dose Selection

A dose of 0.5 mg/kg was estimated as the maximum recommended starting dose (MRSD) for the proposed Phase 1 trial using the lowest value of MRSD determined by two approaches: a traditional HNSTD-based approach (MRSD₁) and a PK-guided approach (MRSD₂).

In brief, using the HNSTD-based approach (CDER 2010), the starting dose was determined as follows. The HNSTD in the GLP toxicology study in cynomolgus monkeys was determined to be 10 mg/kg administered by 10-minute IV infusion every 2 weeks for 2 doses. MRSD₁ was defined as 1/6 the HNSTD ($10 \times 1/6 = 1.67$ mg/kg). The human equivalent of MRSD₁, based on a body surface area conversion factor (CDER 2014), was calculated as 0.53 mg/kg (ie, 1.67 mg/kg \times 0.32). IMGC936 has similar binding affinity (KD) to human and cynomolgus monkey ADAM9 of 1.1 and 1.8 nM, respectively. This slight difference in KD can be attributed to within-assay variability and, therefore, considered to be similar. Consequently, no further adjustment for affinity differential was undertaken. Thus, 0.53 mg/kg dose was considered as the MRSD1.

The second approach for the determination of the starting dose was based on the PK guided approach (Krishnan and Andersen 1990, Mahmood 2009). The HNSTD in the GLP toxicology study in cynomolgus monkeys was determined to be 10 mg/kg and the corresponding predicted area under the curve from time zero to infinity (AUC_{0-inf}) after the administration of the first 10-minute IV infusion dose was 37,089 μ g•h/mL. Using the mean predicted clearance of ADC (CL_{adc}) of 0.00010 L/h/kg in humans, the human equivalent dose producing the same area under

the curve (AUC) at the monkey HNSTD was estimated as 3.71 mg/kg (the product of the AUC in cynomolgus monkeys and the estimated CL_{adc} in humans). To this, a safety factor of 6 was applied as described above resulting in an estimated MRSD2 of 0.62 mg/kg.

The lower of the MRSD1 and MRSD2 values was 0.53 mg/kg. Therefore, 0.5 mg/kg was considered as the MRSD.

The proposed clinical doses for IMGC936 selected for the Phase 1 clinical trial are 0.5, 1.0, 2, 4, 7, 10, and 12 mg/kg administered every 3 weeks as an IV infusion. At the 12 mg/kg dose, the predicted first dose maximum concentration (C_{max}) and AUC for ADC in humans were approximately the same (1×) as the exposure at the HNSTD (10 mg/kg) in monkeys.

2.6.1. Multiples of Monkey Exposure

Allometric scaling, modeling, and simulations were used to estimate exposure data (C_{max} and AUC) in the human after the first dose of 0.5 to 12 mg/kg and compared to the mean cumulative exposure for the HNSTD in the cynomolgus monkey (10 mg/kg). In this estimation, predicted exposure parameters in a dosing interval of 3 weeks (504 hours) in humans after the first dose were compared to actual exposure parameters in a dosing interval of 2 weeks (336 hours) following administration of the second dose at the HNSTD (10 mg/kg). First-dose predicted exposure data suggested adequate multiples of monkey exposure for the proposed dose range (0.5 to 12 mg/kg) to be investigated in humans. Using exposure parameters for ADC, DM51, and total antibody (which includes conjugated and unconjugated antibody), the safety margins at the starting dose of 0.5 mg/kg in humans were 35-, 27- and 25-fold, respectively, based on C_{max} and 64-, 22-, and 67-fold, respectively, and based on cumulative AUC as calculated using human (predicted) and monkey (actual) exposure parameters. Multiples of monkey exposure at the proposed top dose of 12 mg/kg were in the range of 0.3- to 1.4-fold.

3. STUDY OBJECTIVES AND PURPOSE

3.1. Dose Escalation Phase

3.1.1. Primary Objective and Endpoints

- To assess safety and tolerability, including dose-limiting toxicities (DLTs), maximum tolerated dose (MTD), or maximum administered dose (MAD; if no MTD is defined), and recommended Phase 2 dose (RP2D) for IMGC936
 - o Incidence of adverse events (AEs), serious adverse events (SAEs), and DLTs

3.1.2. Secondary Objectives and Endpoints

- To characterize PK and immunogenicity of IMGC936
 - o Study drug concentration
 - Summary PK parameters
 - o Incidence of antidrug antibodies (ADA)
- To describe objective response rate (ORR) and duration of response (DoR) for IMGC936 using Response Evaluation Criteria in Solid Tumors version 1.1 (RECIST v1.1)
 - o ORR
 - o DoR

3.1.3. Exploratory Objectives and Endpoints

- To explore progression-free survival (PFS)
 - o PFS
- To explore potential biomarkers of clinical and/or immunologic response to IMGC936 in blood and tumor tissue
 - o Change in soluble ADAM9 levels over time
 - Correlation of potential biomarkers (FcγR genotype, soluble ADAM9, cell-free tumor DNA) and response
- To explore the relationship between baseline ADAM9 expression and antitumor activity
 - o Correlation of ADAM9 expression and response

3.2. Dose Expansion Phase

3.2.1. Primary Objective and Endpoint

- To describe ORR for IMGC936 using RECIST v1.1
 - o ORR

3.2.2. Secondary Objectives and Endpoints

- To assess safety and tolerability for IMGC936
 - o Incidence of AEs, SAEs, and study drug-related treatment-emergent adverse events (TEAEs) that lead to discontinuation
- To characterize PK and immunogenicity of IMGC936
 - Study drug concentration
 - Summary PK Parameters
 - o Incidence ADA
- To describe DoR and PFS
 - o DoR
 - o PFS

3.2.3. Exploratory Objectives and Endpoints

- To explore potential biomarkers of clinical and/or immunologic response to IMGC936 in blood and tumor tissue
 - o Change in soluble ADAM9 levels over time
 - Correlation of potential biomarkers (FcγR genotype, soluble ADAM9, cell-free tumor DNA) and response
- To explore the relationship between baseline ADAM9 expression and antitumor activity
 - Correlation of ADAM9 expression and response
- To explore ocular primary prophylaxis regimens
 - o Frequency and severity of ocular events

4. INVESTIGATIONAL PLAN

4.1. Overall Study Design and Plan

This study is a Phase 1/2, first-in-human, open-label, dose-escalation and expansion study designed to characterize the safety, tolerability, PK, immunogenicity, and preliminary antitumor activity of IMGC936.

Participants with unresectable, relapsed or refractory, locally advanced or metastatic non-squamous NSCLC, TNBC, CRC, gastroesophageal cancer, or pancreatic cancer will be enrolled globally in approximately 26 centers.

Up to a maximum of 345 participants will be enrolled in the study if all expansion cohorts are fully enrolled.

Each cycle is 21 days for Schedule A and 28 days for Schedule B. IMGC936 is administered via IV infusion at the assigned dose for each cohort. Infusion duration will vary depending on dose and participant tolerability.

Participants may continue on study drug until disease progression, AE requiring discontinuation, withdrawal of consent, physician decision, or other discontinuation criteria are met (Section 5.4).

Participants will be followed for safety throughout the study. Any participant who discontinues study drug should return to the study site for an end of treatment visit (EOTV). The visit should be performed within 30 days following last dose of study drug whenever possible.

4.1.1. Dose Escalation

The primary objective of the Dose Escalation Phase of the study is to characterize safety and tolerability of IMGC936 to define the single-agent MTD and select a RP2D. If no MTD is defined after escalation to the maximum protocol-specified dose, then the highest dose level administered will be designated as the MAD.

Up to 72 evaluable participants will be enrolled in the Dose Escalation Phase of this study.

Dose escalation follows a conventional 3 + 3 design: successive cohorts of 3 to 6 participants each will be evaluated in sequential escalating doses of single-agent IMGC936 (Table 2).

Each cycle is 21 days for Schedule A. IMGC936 is administered via IV infusion on Day 1 of Cycle 1 and every subsequent 21-day cycle thereafter at the assigned dose for each cohort in Schedule A. Infusion duration will vary depending on dose and participant tolerability. Sentinel dosing will be used for the first 2 dose levels. The first administration of IMGC936 (Cycle 1) in participants at the first 2 dose levels of Schedule A dose escalation will be staggered by at least 48 hours.

Upon agreement between investigators and the sponsor, intermediate dose levels may be evaluated based on review of cumulative safety and PK data. For example, participants have been enrolled in intermediate dose cohorts at doses of 5 mg/kg and 6 mg/kg.

Table 2: IMGC936 Dose Levels: Dose Escalation

Cohort	IMGC936 Dose
Cohort 1	0.5 mg/kg
Cohort 2	1.0 mg/kg
Cohort 3	2.0 mg/kg
Cohort 4	4.0 mg/kg
Intermediate Dose	5.0 mg/kg
Intermediate Dose	6.0 mg/kg
Cohort 5	7.0 mg/kg
Cohort 6	10.0 mg/kg
Cohort 7	12.0 mg/kg

Dose escalation will follow standard 3 + 3 design until an MTD or MAD is established. To support the selection of the RP2D, upon agreement between investigators and the sponsor, any dose level not exceeding the MTD may be expanded to a maximum of 15 participants for further evaluation of safety, PK, antitumor activity, to facilitate selection of the RP2D. Intermediate dose levels, not exceeding the MTD, may also be explored.

Participants on Schedule A who are not able to complete the 21-day evaluation secondary to AEs considered unrelated to study drug or any other cause unrelated to study drug are considered unevaluable for safety and toxicity during the DLT evaluation period and may be replaced.

Participants may continue on study drug until disease progression, AE requiring discontinuation, withdrawal of consent, physician decision, or other discontinuation criteria are met (Section 5.4).

If recommended by the Cohort Review Committee, in conjunction with the Sponsor, based on emerging safety, tolerability, PK, and preliminary antitumor activity of IMGC936, an alternate schedule (Schedule B) may be explored (Appendix 2 - Time and Events Schedule (Schedule B - 28 day Cycle). Each cycle is 28 days in contrast to Schedule A, which is 21 days. Participants enrolled on Schedule B will receive study drug on Days 1, 8, and 15 of a 28-day cycle for the first 2 cycles. On all subsequent cycles (Cycle 3 and beyond), participants will receive study drug on Days 1 and 8 of a 28-day cycle (Table 3). To potentially reduce ocular or other safety events that may be driven by C_{max} (maximum drug concentration after infusion), PK modeling suggests a fractionated weekly schedule would allow reduction in C_{max} while maintaining AUC exposure. To reduce participant burden of an indefinite weekly schedule, starting from the third cycle, participants will only receive the study drug in the first 2 weeks in a 4-week cycle.

The 3 + 3 dose escalation as described previously will apply to the alternate schedule. The recommended starting dose of 2 mg/kg/dose (Cycles 1 and 2) and 3 mg/kg/dose (Cycle 3 and beyond) for Schedule B in a 4-week cycle is less than the non-fractionated total dose of 7 mg/kg every 3 weeks, which was administered in Cohort 5 of Schedule A.

Table 3: IMGC936 Dose Levels: Dose Escalation (Schedule B)

Cohort	IMGC936 Dose on Days 1, 8, and 15 of Cycle 1 and Cycle 2	IMGC936 Dose on Day 1 and Day 8 dose of Cycle 3 and beyond
Cohort B1	2 mg/kg/dose	3 mg/kg/dose
Cohort B2	2.5 mg/kg/dose	3.5 mg/kg/dose
Cohort B3	3 mg/kg/dose	3.5 mg/kg/dose
Cohort B4	3.5 mg/kg/dose	4.0 mg/kg/dose

Upon agreement between investigators and the sponsor, intermediate dose levels may be evaluated based on review of cumulative safety and PK data.

Participants on Schedule B who are not able to complete the 28-day evaluation secondary to AEs considered unrelated to study drug or any other cause unrelated to study drug are considered unevaluable for safety and toxicity during the DLT evaluation period and may be replaced.

4.1.2. Expansion Cohorts

The Dose Expansion Phase is designed to explore efficacy of IMGC936 at the RP2D as a single-agent in study participants with relapsed or refractory, unresectable locally advanced or metastatic solid tumors.

RP2D will be selected by the investigators and sponsor. Following determination of the RP2D, and at the sponsor's discretion, up to 7 expansion cohorts may be opened in tumor types selected from those enrolled in dose escalation (Table 4). Participants in Cohorts A through G can be enrolled in either in Dosing Schedule A or Schedule B upon sponsor's discretion.

Table 4: Expansion Cohorts

Cohort	Tumor Type
Cohort A	Non-squamous NSCLC
Cohort B	TNBC
Cohort C	CRC
Cohort D	Gastroesophageal cancer
Cohort E	Pancreatic cancer
Cohort F	Any one above-mentioned tumor with an alternate dose and/or schedule
Cohort G	Any one above-mentioned tumor with an alternate dose and/or schedule

Abbreviations: CRC: colorectal cancer; TNBC: triple-negative breast cancer; NSCLC: non-small cell lung cancer.

Participants may continue on study drug until disease progression, AE requiring discontinuation, withdrawal of consent, physician decision, or other discontinuation criteria are met (Section 5.4).

A futility assessment will be conducted on the first 13 participants (Section 14.1) in each expansion cohort. If there are at least 2 responders out of 13 response-evaluable participants at the first stage, an additional 26 participants may be recruited to that cohort (full expansion) (for a

total of 39 participants) to further evaluate safety, tolerability, PK, immunogenicity, biomarkers, antitumor activity, and survival of participants who received IMGC936.

[figure not shown]
The expansion cohorts may test more than 1 dose and/or schedule, not exceeding the MTD.

Tumor types examined in Cohorts A to E may be further explored at a second dose and/or schedule in Cohorts F and G.

Tumor specimens for determination of ADAM9 expression via IHC staining will be collected from all participants and will be assayed at a central laboratory designated by the sponsor (see Section 10.3.1). ADAM9 testing results are not required for enrollment.

4.1.3. Eye Drop Sub-Study

4.1.3.1. Sub-Study Schema

4.1.3.2. Sub-Study Design

Up to 60 participants from Cohorts A to G may voluntarily consent to join a sub-study to evaluate the effect of different prophylactic eye drops, beyond standard lubricating eye drops. Consenting participants will be assigned to cohorts of 10 to 20 participants who will receive additional eye drops as primary prophylaxis to mitigate ocular symptoms and signs. Participants in this sub-study will be monitored for the frequency and severity of ocular events and will have an ocular examination after 2 cycles of therapy regardless of whether they have ocular symptoms and signs, as required of all participants in this trial. Major differences in ocular AEs (eg, 50% reduction in participants with ≥ Grade 2 keratopathy, or 50% reduction in ocular AEs leading to dose reduction/discontinuation) will be used to determine whether different eye drop regimens provide benefit in comparison to others and to participants on trial that only receive prophylactic lubricating drops. Knowledge gained from this sub-study may be applied to the remainder of the study participants. Details of the eye drop options are described in Section 7.2.1.

4.1.4. Study Assessments

Safety and tolerability will be closely monitored throughout both phases of the study (Section 12).

Additionally, PK and immunogenicity and biomarker assessments will occur as described in Section 10, Appendix 1, and Appendix 4.

Further, antitumor activity is described in Section 11.

4.2. Dose-Limiting Toxicity

For guiding dose-escalation decisions, DLTs will be defined based on TEAEs or abnormal laboratory values that meet DLT criteria that occur up to Day 21 of Cycle 1 for Schedule A and Day 28 of Cycle 1 for Schedule B. AE severity will be graded according to National Cancer Institute (NCI) Common Terminology Criteria for Adverse Events version 5.0 (CTCAE v5.0). DLTs will be defined separately for hematologic, non-hematologic, and hepatic events.

In addition to conventional Cycle 1 DLTs to guide escalation, cumulative toxicity and tolerability for all cohorts will be considered and may be utilized to inform dose escalation.

4.2.1. Hematologic Dose-Limiting Toxicity

Hematologic DLT is defined as follows:

- Grade 4 neutropenia lasting > 7 days
- \geq Grade 3 febrile neutropenia Grade 4 thrombocytopenia, irrespective of duration
- Grade 3 thrombocytopenia associated with clinically significant bleeding
 - \geq Grade 3 hemolysis

The following events will be specifically **excluded** from the definition of hematologic DLT:

- ≥ Grade 3 lymphopenia
- Grade 3 anemia that is not associated with other clinically significant complications

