4.2.3. Hepatic Dose-Limiting Toxicity

Hepatic DLTs will be defined as follows:

- Any elevation of one or more transaminases $> 8 \times$ the institutional reference laboratory upper limit of normal (ULN) irrespective of duration
- Any Grade 3 elevation of one or more transaminases > 5.0–8.0 × ULN that does not resolve to Grade 2 (ie, > 3.0–5.0 × ULN) within 7 days and Grade 1 (ie, > ULN–3.0 × ULN) within 14 days.
- Grade 3 elevation of total bilirubin that is $> 5 \times$ the ULN irrespective of duration
- Any Grade 3 elevation of total bilirubin > 3.0–5.0 × ULN that does not resolve to Grade 2 (ie, > 1.5–3.0 × ULN) within 7 days and Grade 1 (ie, > ULN–1.5 × ULN) within 14 days.
- Any event meeting criteria for Hy's law as follows (all 3 features):
 - Aspartate aminotransferase (AST) and/or alanine aminotransferase (ALT) $> 3 \times ULN$
 - Concurrent elevation of total bilirubin > 2 × ULN without initial evidence of cholestasis
 - No alternative etiology can be identified

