9.8. Clinical Laboratory Tests

Blood and urine samples will be collected per the schedule in Appendix 1 and Appendix 2. Hematology, chemistry, pregnancy, urinalysis, coagulation time, and endocrine evaluation tests will be performed locally. Test results for pregnancy, chemistry, and hematology must be reviewed before study drug administration. For days when only clinical laboratory tests are required (no PK, ADA, or biomarker), participants may have clinical laboratory tests collected at local (non-study site) labs approved by investigator. Laboratory assessment results must be entered into the clinical database.

Clinical laboratory tests to be performed are presented in Appendix 3.

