18. APPENDICES

APPENDIX 1. TIME AND EVENTS SCHEDULE (SCHEDULE A - 21 DAY CYCLE)

	g .			Cycle 1				≥ Cycle 2	2		
EVALUATION/ PROCEDURE	Screening (within 28 days)	Day 1	Day 2	Day 3 (+ 1d)	Day 8 (± 1d)	Day 15 (± 1d)	Day 1 (+ 3d)	Day 8 (± 1d)	Day 15 (± 1d)	EOTV	Follow-up
Informed consent	X										
Eligibility criteria review	X										
Medical/cancer history	X										
Tumor specimen ^a	X										
Physical examination ^b	X	X			X	X	X	X	X	X	
Concomitant medications/procedures			•	(Continuous	S	•	•	•	X	
ECOG performance status-c	X	X					X			X	
12-lead ECG ^d	X	X			X		X			X	
Echocardiogram/MUGA ^e	X									X	
Ophthalmic examination ^f	X				etc.). Par	xams at the ticipants wi Table 7.				X	
Ocular symptoms assessment ^g		X			X	X	X	X	X	X	
Pregnancy test h	X	X					X			X	
Assess for AEs			•	•	•	Continuou	ıs	•	•	•	•
Vital signs i	X	X		X	X	X	X	X	X	X	
Hematology/chemistry j	X	X		X		X	X	X		X	
Coagulation ^j	X	X		X		X	X	X		X	
Endocrine ^j	X									X	
Urinalysis ^j	X	X					X			X	

	Caraanina	Cycle 1 ≥ Cycle 2						2			
EVALUATION/ PROCEDURE	Screening (within 28 days)	Day 1	Day 2	Day 3 (+ 1d)	Day 8 (± 1d)	Day 15 (± 1d)	Day 1 (+ 3d)	Day 8 (± 1d)	Day 15 (± 1d)	EOTV	Follow-up
PK/ADA/Biomarker					S	ee Append	ix 4				
Tumor markers eg, CEA or CA19-9 k	X			Q6W (±	3 days) st	arting Cycl	e 1 Day 1	k		X	
Disease assessment	X		Q6W (±	7 days) w	hile on stu	dy drug the	en Q12W (± 21 days) 1	X¹	
Follow-up assessments m											X ^m
Administer IMGC936		X					X				

Abbreviations: ADA: antidrug antibody; AE: adverse events; C: cycle; CA19-9: carbohydrate antigen 19-9; CEA: carcinoembryonic antigen; D/d: day; ECG: electrocardiography; ECOG: Eastern Cooperative Oncology Group; EOI: end of infusion; EOTV: end of treatment visit; LTFU: lost to follow-up; LVEF: left ventricular ejection fraction; MUGA, multigated acquisition scan; PD: progressive disease; PK: pharmacokinetic; QxW: every x weeks; RECIST: Response Evaluation Criteria in Solid Tumors; RP2D: recommended Phase 2 dose.

- ^a All participants to be enrolled in the study must have an identified formalin-fixed, paraffin embedded tumor specimen or slides as detailed in the laboratory manual; see Section 9.13. Participants may undergo a low-risk, medically routine procedure to obtain a specimen for testing if a suitable archival sample cannot be identified. The specimens will be analyzed retrospectively and will not be used to determine eligibility.

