- b Includes height (screening only) and weight. Weight may be obtained within 24 hours of Cycle 1 Day 1. Full physical examinations are performed at screening, Cycle 1 Day 1 (or within 24 hours before the first infusion), and EOTV. All other physical examinations are directed physical examinations based on symptoms, tumor location, and as clinically indicated. Participants in dose escalation cohorts will have weekly directed physical examination through treatment Cycle 3. Beginning on Cycle 4, physical examination is only required on Day 1 of each cycle. Participants in the dose expansion cohorts should have physical examination recorded on Day 1 of each treatment cycle.
- ^c ECOG performance status should be the primary performance measure for participant enrollment. If ECOG performance status is an inappropriate performance measurement for participant enrollment (eg, chronically nonambulatory), then Karnofsky performance status may be used. A description of the scale is in Appendix 8. ECOG assessment at C1D1 can be performed within 24 hours before the infusion.
- d On Day 1 of Cycle 1, 2 and 3, ECGs are recorded pre-infusion (within 30 minutes before) and EOI (within 30 minutes after EOI). During selected non-dosing visits (eg, screening, C1D8, and EOTV), ECGs will be recorded.
- ^e The Investigator to choose appropriate modality (eg, echocardiogram or MUGA) to assess LVEF.
- ophthalmic examinations are performed at screening by an ophthalmologist per Section 9.12. All participants will have a complete ophthalmological examination when ocular symptoms and signs develop, repeated per Table 7. Participants without ocular symptoms or signs should have an ophthalmic examination at the end of Cycle 2, followed with ophthalmic exams every 3 cycles/ 9 weeks (at the end of Cycle 5,8, etc.) in both dose escalation and expansion phases. Participants with Grade 2 or greater ocular AEs which have not resolved to Grade 1 or baseline must have an ophthalmic examination at EOTV. All other participants are recommended to have an ophthalmic examination at EOTV to document any subclinical findings.
- ^g Ocular symptom assessment at C1D1 can be performed within 24 hours before the infusion. For participants in dose escalation cohorts, ocular symptoms assessment should occur weekly during the first 3 cycles and subsequently Day 1 of each cycle. During the Dose Expansion Phase (at RP2D), if limited ocular

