toxicity is observed during escalation, ocular symptom assessment will occur on Day 1 of each cycle or more frequently if ocular symptoms and signs are observed. Phone-based ocular symptom assessments are acceptable if no clinic visit is scheduled.

- ^h Females of childbearing potential only. Serum pregnancy test is required for eligibility. Subsequent pregnancy tests may use serum or urine. Results must be reviewed before study drug infusion on Day 1 of Cycle 1 and all subsequent cycles. If screening test is performed within 72 hours of first infusion, repeat of the test on Day 1 may be deferred.
- During non-dosing visits (eg, screening and EOTV), vital signs will be taken at one timepoint. For Cycle 1 Day 1, vitals are measured pre-infusion (within 30 minutes before); 15 and 30 minutes after start of infusion (± 5 minutes); EOI (± 10 minutes); and 2, 4, and 6 hours after EOI (± 10 minutes). For Cycle 2 Day 1 and subsequent cycles, vitals are measured pre-infusion (within 30 minutes before), EOI (± 10 minutes), and 1 hour after EOI (± 10 minutes). Participants in dose escalation cohorts must have vital signs recorded on both dosing and non-dosing days through treatment Cycle 3. Beginning on Cycle 4, vital signs must be recorded on Day 1 of each treatment cycle. Participants in expansion cohorts must have vital signs recorded on Day 1 of each treatment cycle.
- ^j To be obtained pre-infusion. Day 1 laboratory samples can be obtained up to 3 days before infusion. Chemistry and hematology results must be reviewed before study drug administration. See Appendix 3 for assessments. Beginning on Cycle 4, laboratory samples only required on Day 1 of each cycle.
- ^k Tumor markers are obtained as indicated for each specific tumor type, eg, CEA for colorectal cancer and CA19-9 for pancreatic cancer. Repeat collection on Cycle 1 Day 1 if screening collection > 7 days prior.
- Tumor assessments are Q6W (\pm 7 days) while participant is on study drug, then Q12W (\pm 21 days). Assessments continue until discontinuation criteria are met. Tumor assessments are performed at EOTV except if prior assessment was \leq 30 days of EOTV and results are available for RECIST v1.1 assessment.
- ^m Tumor assessments will occur after participant has discontinued study drug Q12W (± 21 days) until evidence of PD, initiation of another anticancer therapy, withdrawal of consent, LTFU, death, or end of study, whichever occurs first.

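### Schedule A schedules no hematology or chemistry between Cycle 1 Days 3 and 15, so a silent laboratory DLT can come and go unsampled; a Day 8 sample would cheaply narrow the gap (minor priority)

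*Protocol*

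**What the plan says.** Protocol Section 4.2 makes laboratory values part of the DLT definition for Schedule A: "DLTs will be defined based on TEAEs or abnormal laboratory values that meet DLT criteria that occur up to Day 21 of Cycle 1". Three laboratory DLTs carry no duration condition:

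- Section 4.2.1: "Grade 4 thrombocytopenia, irrespective of duration".
- Section 4.2.3: transaminases > 8 x "the institutional reference laboratory upper limit of normal (ULN) irrespective of duration".
- Section 4.2.3: total bilirubin > 5 x "the ULN irrespective of duration".

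In Appendix 1 the row "Hematology/chemistry j" is marked in Cycle 1 on Days 1, 3 and 15 and is blank on Days 2 and 8. From Cycle 2 it is marked on Days 1 and 8. The blank is not a shifted column: physical examination, vital signs and ocular symptoms are marked at Cycle 1 Day 8, and footnote d names that visit: "During selected non-dosing visits (eg, screening, C1D8, and EOTV), ECGs will be recorded". Appendix 4 also takes a PK sample on Cycle 1 Day 8. Schedule B (Appendix 2) samples hematology and chemistry on Day 8 of Cycle 1, which is a dosing day there.

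No other text supplies the missing sample. Footnote j and Section 9.8 require review of results before dosing ("Chemistry and hematology results must be reviewed before study drug administration"), which concerns the next dose, not Day 8.

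**The concern.** A DLT that counts whatever its duration can be counted only if blood is drawn while the value is abnormal, or if symptoms prompt a test. The extra monitoring in Sections 7.4.1 and 7.7 starts only once an abnormal value has been seen.

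Pre-dose review at Cycle 2 Day 1 catches values that have not recovered. What it cannot catch is a silent event that has recovered by then. That participant is re-dosed at the same dose. Had the event been seen, the protocol would call for discontinuation for a DLT in escalation (Section 5.4), permanent discontinuation for transaminases > 8 x ULN (Section 7.4.1), or a hold, weekly counts and a one-level reduction for Grade 4 thrombocytopenia or neutropenia (Section 7.7). Hematologic toxicity is a listed potential risk of the drug (Section 2.4). Any further Schedule A escalation decision could also rest on too few counted DLTs.

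**Working it through.** The documents state no detection figure, so there is none to reproduce.

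**Inputs.** Appendix 1: Cycle 1 draws on Day 1, Day 3 (+1 day) and Day 15 (±1 day); the Day 8 visit has ±1 day. The Cycle 2 Day 1 draw is nominally study Day 22. With the +3-day visit window and footnote j (labs up to 3 days before infusion) it can fall on Days 19-25. Onset and duration are not given. I assume onset uniform over the 21 days of the DLT window and show several durations.

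**Gap.** Nominal: 15 − 3 = 12 days. With windows: 14 − 4 = 10 to 16 − 3 = 13. With Day 8 added, the longest nominal gap is 15 − 8 = 7.

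**Unsampled onset days.** Between draws on Days a and b, an L-day episode has max(0, b − a − L) onset days with no draw. Onsets are limited to Day 21. If the Cycle 2 draw is on Day 19 or 20, the onset days left after it, up to Day 21, are added. Later Cycle 2 draws are not counted.

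Nominal days, now:

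- 5-day: (12 − 5) + (7 − 5) = 9/21 = 43% (Days 4-10 and 16-17).
- 3-day: (12 − 3) + (7 − 3) = 13/21 = 62%.
- 8-day: 12 − 8 = 4/21 = 19% (Days 4-7).

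Nominal days, with Day 8:

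- 5-day: 0 + (7 − 5) + (7 − 5) = 4/21 = 19%.
- 3-day: (5 − 3) + (7 − 3) + (7 − 3) = 10/21 = 48%.
- 8-day: 0/21.

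All windows together, including the Cycle 2 draw on Days 19-25:

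| Episode | Now | With Day 8 |
|---|---|---|
| 5-day | 7-12/21 (33-57%) | 2-8/21 (10-38%) |
| 8-day | 2-7/21 (10-33%) | 0-3/21 (0-14%) |

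For example, the 5-day maximum now has draws on Days 3, 16 and 25: (13 − 5) + (9 − 5) = 12. The 5-day maximum with Day 8 has draws on Days 3, 7, 16 and 25: 0 + (9 − 5) + (9 − 5) = 8.

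The 8-day row bears on Grade 4 neutropenia, which is a DLT only beyond 7 days (Section 4.2.1). Here it concerns detection, not proof of duration.

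**3+3 illustration.** Under Section 4.4, P(escalate) = (1 − p)³ + 3p(1 − p)⁵. I assume a true DLT rate of 0.33, which gives 0.434 with full detection. If a share s of DLTs is silent, the observed rate is 0.33 × (1 − s × missed fraction). With the nominal fractions above:

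| Silent share | Episode | Now | With Day 8 | Difference (points) |
|---|---|---|---|---|
| 5% | 3-day | 0.454 | 0.450 | 0.5 |
| 25% | 3-day | 0.538 | 0.513 | 2.5 |
| 25% | 5-day | 0.505 | 0.465 | 4.0 |
| 50% | 5-day | 0.580 | 0.497 | 8.3 |

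The result is sensitive to assumed onset as well. Placing all silent onsets between Days 3 and 15 changes the last row to 0.635 against 0.489. The documents give neither the share nor the onset pattern.

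**The case against.** The best case for leaving the schedule alone has four parts.

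- **Little Schedule A escalation may remain.** Section 4.1.1 records that 5, 6 and 7 mg/kg have been given, and SAP Section 7 names 6 mg/kg as the recommended dose. Table 2 still lists 10 and 12 mg/kg, but nothing says they are planned. Expansion is monitored under Section 4.3, not by the 3+3 rule. This stands, and it limits the trial-level effect.
- **The silent share may be small.** Section 7.2 reports ocular events in patients, which this gap does not affect. Monkey clinical pathology changes were transient and mild (Section 2.5.1.2), and hepatic toxicity is not among the risks in Section 2.4. This also stands.
- **Some events would show.** Escalation participants have a directed physical examination at Day 8, including the whole skin (Section 9.6). Jaundice or skin bleeding could prompt a test. This is partial cover: it would not reveal a silent transaminase rise, and Section 9.6 requires an examination of Schedule A expansion participants only on Day 1 of each cycle.
- **Other safeguards exist.** Pre-dose review, optional repeat tests (Section 12.2.1) and use of data beyond the DLT period (Section 4.4) all help. None of them samples an event that was silent and has recovered.

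A reader might infer that the protocol contradicts itself, or that past dose decisions and the 6 mg/kg choice are unsound. The documents support neither. No text promises weekly Cycle 1 laboratory tests, so the blank cell is a design choice. No DLT counts or laboratory data are given that would show an event was missed.

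**Conclusion.** The point holds as a low-cost improvement of minor priority. The 12-day gap (10 to 13 with windows) is read directly from Appendix 1 and rests on no assumption. The miss rates do: they need uniform onset over Days 1-21, a fixed episode length and a silent event. On nominal days an episode of 12 days or more is always sampled; with draws on Days 3 and 16, a 12-day episode (Days 4-15) can still hide.

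The benefit is prospective and mainly individual dose safety for remaining Schedule A participants: dose levels expanded to 15, expansion cohorts on Schedule A, and any further escalation. Under uniform onset, the change in 3+3 escalation probability runs from about 0.5 to 8 points for silent shares of 5-50%. That range is illustrative, and it should not be read as an estimate of bias in decisions already made.

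**What to change.** In Appendix 1, mark the hematology/chemistry cell at Cycle 1 Day 8 and leave the DLT definitions as they are. The visit and the PK draw already exist, and the change matches Schedule A from Cycle 2 and Schedule B in Cycle 1.

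It does not close the gap. Short episodes can still fall between draws, and the interval from Day 15 to Cycle 2 Day 1 is untouched. A Day 8 result can detect Grade 4 neutropenia and start the weekly counts of Section 7.7.1, but one draw does not document a duration beyond 7 days. It also does not repair past escalation decisions.

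The cost is one routine sample per participant and one amended table cell. Section 16.1 requires IRB/IEC approval where applicable, across about 26 centers, so the change is best carried in the next amendment.
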